10.2 Recording Adverse Events/ Treatment being studied

CTCAE term (AE description) and grade: The descriptions and grading scales found in the revised NCI Common Terminology Criteria for Adverse Events (CTCAE) version 5.0 will be utilized for AE reporting. All appropriate treatment areas should have access to a copy of the CTCAE version 5.0. A copy of the CTCAE version 5.0 can be downloaded from the CTEP web site:

10.21 Adverse event monitoring and reporting is a routine part of every clinical trial. First, identify and grade the severity of the event using the CTCAE version 5.0. Next, determine whether the event is expected or unexpected and if the adverse event is related to the study procedure. With this information, determine whether the event must be reported as an expedited report (see Section 10.25).

Expedited and routine reports are to be completed within the timeframes and via the mechanisms specified in Sections 10.4 and 10.6. All expected AE reports must also be sent to the local Institutional Review Board (IRB) according to local IRB's policies and procedures.

10.211 When assessing whether an adverse event (AE) is related to a medical agent(s) medical or procedure, the following attribution categories are utilized:

Definite - The AE *is clearly related* to the agent(s)/procedure.

Probable - The AE *is likely related* to the agent(s)/procedure.

Possible - The AE *may be related* to the agent(s)/procedure.

Unlikely - The AE *is doubtfully related* to the agent(s)/procedure.

Unrelated - The AE *is clearly NOT related* to the agent(s)/procedure.

10.22 Exceptions to Expedited Reporting

An expedited report may not be required for specific Grade 1, 2 and 3 serious Adverse Events. Any protocol specific reporting procedures **MUST BE SPECIFIED BELOW** and will supersede the standard Expedited Adverse Event Reporting Requirements: **Hospitalizations for reasons deemed to be disease or SOC related will not be reported.**

10.23 Solicited Adverse Events Grade 2 or higher:

Dyspnea
Conduction disorders
Chest pain/cardiac pain
Congestive Heart Failure
Myocardial infarction
Myocarditis
Pericardial effusion
Pericarditis
Lung Adverse Events
Gastrointestinal Adverse Events

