11.0 Treatment Evaluation/Measurement of Effect

This will be measured based on retrospective clinical outcomes.

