11.1 Effectiveness Outcome Measures

Cardiac Events:

Any cardiac event after registration including electrophysiological changes as defined by the continuous insertable cardiac monitor (ICM); CHF; Myocardial infarction; pericarditis or myocarditis; cardiac ablation or cardiac pacemaker; cardiac stent placement or any coronary procedure for coronary damage; or any cardiac event as defined by the patients’ medical records or autopsy if done.

Cardiac event determined by the ICM would include: Bradycardia: asystole > 3 seconds, bradycardia HR < 40 bp; Tachy: HR > 150 bpm for any number of beats; Atrial Fibrillation lasting ≥ 8 seconds. Post-mortem device interrogation will be performed when possible in cases of patient death and included as per ICM criteria. Patients will undergo limited chest autopsy, if they agree and consent.

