16.0 Statistical Considerations and Methodology

16.1 Study Design

This is a single-arm, observational study designed to determine the 12-month cardiac event rate after radiation or chemo-radiation for thoracic malignancies meeting the eligibility criteria.

16.11 Primary Endpoint:

A cardiac event will be defined according to section 11.1 and occurring during the first 12 months after radiation or chemo-radiation. An evaluable patient will be classified as a failure (cardiac event) for the primary endpoint if the patient had any of the events listed in section 11.1 during the time period. All patients meeting the eligibility criteria who have signed a consent form, have begun RT, and have not experienced a major treatment violation within the first month of treatment will be evaluable for response.

16.2 Statistical Design:

This is an observational study intended to provide preliminary estimates of cardiac event rate in patients receiving radiation or chemo-radiation. Safety of the implanted cardiac monitoring device will be described. Point estimates and two-sided 95% confidence intervals will be computed. All patients meeting the eligibility criteria who have signed a consent form and have begun treatment will be included in the descriptive estimates.

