16.32 Definitions and Analyses of Secondary Endpoints

16.321 Analysis Plan

The analysis for this trial will commence when 24 patients have either died or reached the 12 month data point. Cardiac event as recorded in section 11.1 would be used for our analysis. We expect to see 3 or more cardiac events grade 3 or higher based on the CTC AE V5.0.

16.322 The following definitions are used for the secondary endpoints of interest:

All end points would be measured studied from the date of patient registration

- Acute adverse events: all AEs occurring within the first 6 months from the date of enrollment.
- Late adverse events: all AEs occurring after the first 6 months from the date of enrollment.
- Loco-regional recurrence: local recurrences of the cancer in the same location where the disease was found on any diagnostic or staging study.
- Distant recurrence: metastatic cancer that has either been biopsy confirmed or clinically diagnosed as recurrent.
- Disease- free survival: the time from study registration any local, regional, distant failure, or death.
- Cause specific survival: the time from registration to death due to cancer. If the cause of death is unknown or difficult to establish,

patients with a distant failure at the time of death would be censored as dying from cancer.

- Cardiac event free survival: the time from registration to cardiac event or death.
- Cardiac death: the time from registration to death due to cardiac reasons. Cardiac death would include documented congestive heart failure, myocardial infarction, arrhythmia*, heart block*, or any other cardiac cause documented in the medical records, death certificate, or autopsy as one of the major contributing causes of death.

*Any lethal electrophysiologic change documented by the ICD before death would also be included.

- Overall survival: the time from registration to death due to any cause.

16.323 Adverse events: All eligible patients that have initiated treatment will be considered evaluable for assessing adverse event rate(s). The maximum grade for each type of adverse event will be recorded for each patient, and frequency tables will be reviewed to determine patterns. Additionally, the relationship of the adverse event(s) to the study treatment will be taken into consideration.

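### Cardiac terms are solicited only from grade 2, while the endpoint and the AE tables count every grade, so grade 1 cardiac events outside the ICM may be ascertained unevenly

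*Combined protocol and SAP*

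**What the plan says.** **What is counted.** Section 11.1 defines the outcome as "Any cardiac event after registration including electrophysiological changes as defined by the continuous insertable cardiac monitor (ICM"), together with heart failure, infarction, pericarditis or myocarditis, cardiac procedures, and any cardiac event found in the medical records or at autopsy. Section 16.11 makes a patient a failure "if the patient had any of the events listed in section 11.1 during the time period". Neither sets a CTCAE grade. Section 16.322 defines "Acute adverse events: all AEs occurring within the first 6 months from the date of enrollment" and "Late adverse events: all AEs occurring after the first 6 months from the date of enrollment", and 16.323 takes the maximum grade of each type per patient.

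**What is actively sought.** Section 10.23 is headed "Solicited Adverse Events Grade 2 or higher". It names dyspnea, conduction disorders, chest or cardiac pain, heart failure, infarction, myocarditis, pericardial effusion and pericarditis, plus lung and gastrointestinal events.

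**How it is gathered.** Section 11.0 says of the effect: "This will be measured based on retrospective clinical outcomes". Section 1.5 has patients followed prospectively in a registry, draws data from the medical records and requires no study-specific visits. Table 5.0 marks an AE assessment before treatment, during treatment, at 4 weeks, at 3, 9 and 12 months, and at unscheduled visits. Section 10.21 asks that events be identified and graded by CTCAE 5.0. Neither Table 5.0 nor 10.21 has a grade floor.

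**The concern.** The rule for counting and the rule for asking do not match. The analysis sections treat every grade as in scope, but the one list that tells site staff which cardiac terms to ask about starts at grade 2. A grade 1 cardiac finding that the ICM does not record therefore depends on whether someone raised it at the AE visit or wrote it in the chart. Two patients with the same mild finding could be classified differently.

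Goals 2.21 and 2.22 ask for the spectrum of cardiac toxicity, its timeline, and early findings that predict permanent damage. The mildest events are the early end of that spectrum, and they are the ones the plan seeks least systematically.

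**Working it through.** The plan gives no figure on this point: no rate of grade 1 cardiac events, no rate of ICM-positive patients and no capture rate. The check is therefore mainly a comparison of sections, followed by an illustration on stated assumptions.

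**Step 1. Sections side by side.**

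| Use | Section | Grade floor |
|---|---|---|
| Primary endpoint | 11.1, 16.11 | none |
| Acute and late AEs | 16.322 | none |
| AE tables by maximum grade | 16.323 | none |
| AE assessment at visits | Table 5.0 | none |
| Grading of AEs | 10.21 | none |
| Solicited cardiac terms | 10.23 | grade 2 |

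Only 10.23 has a floor. It governs what is asked, not what may be recorded. No section says that grade 1 events are left out.

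**Step 2. Effect on the primary rate.** Let *r* be the share of patients with an ICM event, *g* the share with a grade 1 cardiac event outside the ICM, and *u* the share of those events neither elicited nor charted. If these are independent, and if other qualifying non-ICM events are ignored:

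understatement of the patient-level rate = (1 − r) × g × u

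Assume g = 10% to 20% and u = 50% to 100%. None of these values comes from the documents.

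| r (assumed) | Low: g = 10%, u = 50% | High: g = 20%, u = 100% |
|---|---|---|
| 10% | 0.9 × 0.10 × 0.5 = 4.5 points | 0.9 × 0.20 × 1 = 18 points |
| 30% | 0.7 × 0.10 × 0.5 = 3.5 points | 0.7 × 0.20 × 1 = 14 points |
| 50% | 0.5 × 0.10 × 0.5 = 2.5 points | 0.5 × 0.20 × 1 = 10 points |
| 70% | 0.3 × 0.10 × 0.5 = 1.5 points | 0.3 × 0.20 × 1 = 6 points |

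For scale, one patient in 24 is 1/24 = 4.2 points. The high column is a limit rather than an estimate: u = 100% would mean that no grade 1 event is ever noted at any AE visit or in any chart. Counting the ignored non-ICM events would lower every cell.

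**Step 3. Effect on the AE tables.** Here an ICM event does not stand in for a missed grade 1 term, so the factor (1 − r) drops out. The loss is g × u, from 0.10 × 0.5 = 5 points (1.2 of 24 patients) to 0.20 × 1 = 20 points (4.8 of 24), whatever r is. The AE tables are thus more exposed than the primary rate on the same assumptions.

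**Step 4. Is r likely to be high?** Section 11.1 counts "Tachy: HR > 150 bpm for any number of beats; Atrial Fibrillation lasting ≥ 8 seconds", as well as asystole over 3 seconds and a heart rate below 40. These are low thresholds over about 14 months of monitoring (section 4.0), so r may well lie toward the lower rows of the table. That is a judgement. It assumes that the device captures rhythms at the thresholds of 11.1; the automatic storage criteria in section 4.0 are stricter (for example, a pause of at least 4.5 seconds, and tachycardia of at least 16 beats). Footnote 7 of Table 5.0 also allows implantation after RT has started.

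**The case against.** The strongest reply is that a solicited list is not a collection floor. AE assessment is scheduled in every column of Table 5.0, grading has no floor, and section 10.1 requires new clinically significant findings that meet the AE definition to be recorded at the end of the study. The primary endpoint does not depend on 10.23 at all, since 11.1 accepts any cardiac event in the medical records and every ICM event. All of this stands, and it limits the point to uneven ascertainment.

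Four stronger readings are tempting and are not supported:

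- A reader might infer that grade 1 cardiac events are not collected, so that toxicity is certainly under-counted. No section bars recording them.
- A reader might take 11.0 to mean that everything outside the ICM is chart review after the fact. Section 1.5 and Table 5.0 describe prospective follow-up with scheduled assessments; 11.0 is one sentence that needs reconciling with them.
- A reader might infer that arrhythmia or cardiac arrest is missed because 10.23 does not name it. Rhythm events are what the ICM is there to detect, and sudden death is reportable under 10.32.
- A reader might point to a small effusion on a scheduled echocardiogram or MRI as a lost grade 1 event. The documents do not reproduce the CTCAE criteria, so its grade cannot be shown from them.

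What remains is that Table 5.0 and 10.21 point one way and 10.23 another. Site staff cannot tell from the plan whether grade 1 cardiac terms must be asked about.

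**Conclusion.** The mismatch is real and worth correcting, but it does not undermine the primary analysis. Grade 1 cardiac events outside the ICM may be ascertained inconsistently, chiefly in the descriptive AE tables and in the material for goals 2.21 and 2.22. The effect on the primary rate is probably small, on the assumption that many patients will already be failures through a low-threshold ICM event or a charted cardiac event. The documents do not allow its size to be computed. The ranges in the working rest on assumed values of r, g and u and show only how the effect shrinks as ICM positivity rises; they should not be quoted as an estimate of bias.

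**What to change.** 1. In 10.23, solicit the cardiac terms at any grade, with onset date, at the AE visits already in Table 5.0.
2. Reconcile the sentence in 11.0 with the prospective follow-up in 1.5 and the visit schedule in Table 5.0, so that the role of chart review is clear.
3. Show primary events by grade and by source (ICM or non-ICM). Section 16.321 already anticipates events of grade 3 or higher, so grades will be needed anyway. The split lets a reader see how far the rate rests on mild events outside the device.
4. Leave the definition in 16.322 unchanged for the other terms. A grade 2 limit on those tables would discard data now in scope.

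The cost is a slightly longer AE form and more minor events to record for about 24 patients, at visits that already exist, plus wording changes in 10.23, 11.0 and the reporting of the primary endpoint. No sample-size change follows.

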10.3 Other Required Reporting

10.31 Unanticipated Problems Involving Risks to Subjects or Others (UPIRTSOS)

Unanticipated Problems Involving Risks to Subjects or Others (UPIRTSOS) in general, include any incident, experience, or outcome that meets **all** of the following criteria:

1. Unexpected (in terms of nature, severity, or frequency) given (a) the research procedures that are described in the protocol-related

documents, such as the IRB-approved research protocol and informed consent document; and (b) the characteristics of the subject population being studied;

2. Related or possibly related to participation in the research (in this guidance document, possibly related means there is a reasonable possibility that the incident, experience, or outcome may have been caused by the procedures involved in the research); and
3. Suggests that the research places subjects or others at a greater risk of harm (including physical, psychological, economic, or social harm) than was previously known or recognized.

Some unanticipated problems involve social or economic harm instead of the physical or psychological harm associated with adverse events. In other cases, unanticipated problems place subjects or others at increased *risk* of harm, but no harm occurs.

Note 1: If there is no language in the protocol indicating that pregnancy is not considered an adverse experience for this trial, and if the consent form does not indicate that subjects should not get pregnant/impregnate others, then any pregnancy in a subject/patient or a male patient's partner (spontaneously reported) which occurs during the study or within.

Note 2: research procedures include: cardiac monitoring device placement and extraction, cardiac monitoring employing the cardiac monitoring device, cardiac MRI, dried blood collection, and blood biobanking. Cancer treatment is per SOC and at the discretion of the treating physicians and not part of the research procedures. Expected toxicities as part of the SOC cancer treatment will not be considered for IRB reporting.

10.32 Death

Note: A death on study requires both routine and expedited reporting regardless of causality, unless as noted below. Attribution to treatment or other cause must be provided.

Any death occurring within 30 days of the last dose, regardless of attribution to an agent/intervention under an IND/IDE requires expedited reporting within 24-hours.

Any death occurring greater than 30 days with an attribution of possible, probable, or definite to an agent/intervention under an IND/IDE requires expedited reporting within 24-hours.

Reportable categories of Death

- Death attributable to a CTCAE term.
- Death Neonatal: A disorder characterized by cessation of life during the first 28 days of life.
- Death NOS: A cessation of life that cannot be attributed to a CTCAE term associated with Grade 5.
- Sudden death NOS: A sudden (defined as instant or within one hour of the onset of symptoms) or an unobserved cessation of life that cannot be attributed to a CTCAE term associated with Grade 5.
- Death due to progressive disease should be reported as **Grade 5 “Neoplasms benign, malignant and unspecified (including cysts and polyps) – Other (Progressive Disease)”** under the system organ class (SOC) of the same name. Evidence that the death was a manifestation of underlying disease (e.g., radiological changes suggesting tumor growth or progression: clinical deterioration associated with a disease process) should be submitted.

10.5 Monitoring and Auditing

The investigator will permit study-related monitoring, audits, and inspections by the IRB, and government regulatory agencies, of all study related documents (e.g. source documents, regulatory documents, data collection instruments, study data etc.). The investigator will ensure the capability for inspections of applicable study-related facilities (e.g. pharmacy, diagnostic laboratory, etc.). Participation as an investigator in this study implies acceptance of potential inspection by government regulatory authorities and applicable compliance offices

10.51 Medical Monitoring

It is the responsibility of the Principal Investigator to oversee the safety of the study at his/her site. This safety monitoring will include careful assessment and appropriate reporting of adverse events as noted above, as well as the construction and implementation of a site data and safety-monitoring plan (see section 10.7 “Monitoring and Auditing”). Medical monitoring will include a regular assessment of the number and type of

serious adverse events. “Any serious adverse events will be followed up by the sentinel event reporting procedure”

10.52 Internal Data and Safety Monitoring Board

The trial will be reviewed by the Cancer Center Auditing area on a bi-annual or yearly basis dependent on random study selection to assess accrual, adverse events, and any endpoint problems. Any safety issues requiring protocol changes will be communicated through protocol amendments.

11.0 Treatment Evaluation/Measurement of Effect

This will be measured based on retrospective clinical outcomes.

11.1 Effectiveness Outcome Measures

Cardiac Events:

Any cardiac event after registration including electrophysiological changes as defined by the continuous insertable cardiac monitor (ICM); CHF; Myocardial infarction; pericarditis or myocarditis; cardiac ablation or cardiac pacemaker; cardiac stent placement or any coronary procedure for coronary damage; or any cardiac event as defined by the patients’ medical records or autopsy if done.

Cardiac event determined by the ICM would include: Bradycardia: asystole > 3 seconds, bradycardia HR < 40 bp; Tachy: HR > 150 bpm for any number of beats; Atrial Fibrillation lasting ≥ 8 seconds. Post-mortem device interrogation will be performed when possible in cases of patient death and included as per ICM criteria. Patients will undergo limited chest autopsy, if they agree and consent.

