⁶ Patient care costs covered by Mayo Clinic Cardiology

⁷ Highly recommended before the start of RT. If this is not clinically possible due to scheduling, conduct as soon as possible after the start of RT

^r Indicates paid by research

After enrollment and prior to initiation of RT or CRT, cardiac testing will be per SOC at our Cardio-Oncology Clinic (e.g. ECG, strain echocardiography, cardiac MRI). Pulmonary function tests would also be obtained per SOC. ICM will be inserted subcutaneously by a cardiologist in the left para-sternal area, using standard sterile technique with local anesthesia. Risks of this insertion are truly minimal but may include bleeding or infection. For reference, this in-office minimally invasive procedure is analogous to the upper arm Implanon/Nexplanon® birth control implant. Whole blood samples will be drawn via peripheral blood draw and biobanked. Dried blood spots will be collected at home by patients and returned for analysis. For reference, the approach for dried blood spot collection is analogous to a finger prick blood glucose check. Dried blood spot collection would only require a single finger prick at each time point and would be truly minimal risk but may carry very low risk of infection. STANDARD OF CARE cardiac testing, STANDARD OF CARE pulmonary function tests, and peripheral blood draw for whole blood biobanking will be performed at STANDARD OF CARE follow-up appointments after RT, including 4 weeks after RT, 3 months after RT, 9 months after RT, and 12 months after RT. Data from the ICM will be collected via wireless data transfer. Data will be transferred on scheduled monthly remote follow-ups or unscheduled in case there is a rhythm alert notification automatically sent (when the arrhythmia event meets pre-determined criteria). The follow-up data will be monitored by the Mayo Clinic Cardiac Implantable Electronic Devices Remote Follow-up Clinic. Alerts from any devices are monitored within 24 hours, 365 days per year uninterrupted. All abnormal cardiac rhythm strips are initially adjudicated by a Certified Cardiac Device Specialist Registered Nurse and confirmed by a cardiac electrophysiologist. The programmed criteria for automatic arrhythmia storage is: sinus bradycardia ≤ 30 bpm for ≥ 8 seconds, sinus arrest with pauses ≥ 4.5 seconds, and 2nd or 3rd degree AV block ≤ 30 bpm lasting ≥ 8 seconds. Tachycardia is defined as a heart rate ≥ 150 bpm for ≥ 16 beats. Sustained VT is defined as lasting ≥ 30 seconds. Post-mortem device interrogation will be performed in cases of patient death. Patients will undergo limited chest autopsy, if they agree and consent.

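### The ICM thresholds that define the primary endpoint (section 11.1) are wider than the stated device storage criteria (section 4.0), so the ICM part of the 12-month event rate is biased low by an amount the documents do not allow to be computed

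*Combined protocol and SAP*

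**What the plan says.** Section 4.0 (Test Schedule) describes how the monitor is set: "The programmed criteria for automatic arrhythmia storage is: sinus bradycardia ≤ 30 bpm for ≥ 8 seconds, sinus arrest with pauses ≥ 4.5 seconds". The same list adds AV block of the second or third degree, at a rate of at most 30 bpm for at least 8 s. A separate sentence follows that list: "Tachycardia is defined as a heart rate ≥ 150 bpm for ≥ 16 beats". Section 4.0 states no storage criterion for atrial fibrillation (AF). Data are transferred monthly, or sooner if an alert is triggered, and abnormal strips are adjudicated by a device nurse and an electrophysiologist.

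Section 11.1 (Effectiveness Outcome Measures) defines the ICM events differently: "asystole > 3 seconds, bradycardia HR < 40 bp; Tachy: HR > 150 bpm for any number of beats". Its AF criterion comes next and has a minimum duration: "Atrial Fibrillation lasting ≥ 8 seconds". It also admits clinical events such as heart failure, infarction or pacemaker placement, and "any cardiac event as defined by the patients’ medical records or autopsy if done".

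Section 16.11 ties the primary endpoint to section 11.1. An evaluable patient is a failure "if the patient had any of the events listed in section 11.1 during the time period". Section 16.31 repeats the link to section 11.

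**The concern.** A patient should be classifiable from the data that the study sets out to record. Here the endpoint uses one set of thresholds and the recorder is programmed with a narrower one, and no section says how an episode lying between them would be recorded. Section 1.3 justifies the implant on the ground that conduction disorders are often brief and silent. Those are the episodes least likely to enter the endpoint through symptoms or the medical record if the device does not store them.

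At stake is the meaning of the reported 12-month rate. It would be neither the section 11.1 rate nor the rate of episodes meeting the section 4.0 criteria, and two analysts could classify the same patient differently. With 18 patients in the power statement, each reclassified patient moves the proportion by 1/18, about 5.6 percentage points.

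**Working it through.** **Step 1. The two sets of thresholds side by side.**

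| Rhythm | Section 4.0 | Section 11.1 | Counted by 11.1 but outside 4.0 |
|---|---|---|---|
| Pause | ≥4.5 s (storage) | >3 s | >3 to <4.5 s |
| Bradycardia | sinus, ≤30 bpm for ≥8 s (storage) | <40 bpm, no duration | >30 to <40 bpm; also ≤30 bpm for <8 s, unless it contains a pause ≥4.5 s |
| AV block | 2nd/3rd degree, ≤30 bpm for ≥8 s (storage) | not named in the ICM list; enters through rate or pause | as for bradycardia |
| Tachycardia | ≥150 bpm for ≥16 beats (worded as a definition) | >150 bpm, no minimum run | runs of 1 to 15 beats |
| AF | nothing stated | ≥8 s | cannot be determined |

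The only difference in the other direction is a rate of exactly 150 bpm, which meets ≥150 but not >150. The pause and bradycardia rows rest on explicit storage settings. The tachycardia row is a conflict of definitions. The AF row is an omission.

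**Step 2. The plan's own figure.** Section 16.22 gives 18 patients, 80% power, one-sided alpha 0.10, and rates of 1% and 10%. By the normal approximation with null and alternative variances:

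n = [(1.2816 × √(0.01 × 0.99) + 0.8416 × √(0.10 × 0.90)) / (0.10 − 0.01)]² = [(0.1275 + 0.2525) / 0.09]² = 17.8, rounded up to 18. Power at 18 is 80.2%, so the figure reproduces.

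**Step 3. Illustration of under-capture.** Let g be the share of event patients whose only qualifying episodes lie in the gap and are not recovered by any other route. The documents give no value for g, so a range is assumed. The true section 11.1 rate is assumed to be 10%.

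- Expected observed rate: 0.10 × (1 − g)
- Expected count among 18: 18 × 0.10 × (1 − g)
- Chance of at least one captured event: 1 − [1 − 0.10 × (1 − g)]^18

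| g | Observed rate | Expected count | P(at least 1 of 18) |
|---|---|---|---|
| 0 | 10% | 1.80 | 1 − 0.900^18 = 85% |
| 25% | 7.5% | 1.35 | 1 − 0.925^18 = 75% |
| 50% | 5% | 0.90 | 1 − 0.950^18 = 60% |
| 75% | 2.5% | 0.45 | 1 − 0.975^18 = 37% |

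The proportional loss is the same at any true rate. At an assumed 30%, the expected count among 18 falls from 5.4 to 4.05, 2.7 and 1.35.

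The last column is not the power of the plan's test. The protocol states no decision count, and at a 1% rate the chance of one or more events in 18 is 1 − 0.99^18 = 16.5%, above the stated alpha of 0.10.

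**The case against.** The strongest reply is that the endpoint is a patient-level composite. One event of any kind is enough, and heart failure, infarction, procedures, medical-record diagnoses and autopsy findings do not depend on ICM storage. Scheduled recordings, and ECG or Holter where done, can also catch an episode. A patient with a gap episode and any other qualifying event is classified correctly. This stands, and it limits the problem to patients with nothing but unrecovered gap episodes. A reader might infer that the device will miss many events, or that the endpoint cannot be ascertained at all. The documents support neither reading, because they give no frequency for gap episodes and they provide several other routes into the endpoint.

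A reader might also infer that runs under 16 beats and all AF go unstored. Section 4.0 does not say so. Its tachycardia sentence comes after the storage list and is worded as a definition. On AF it is silent, while section 1.4 cites 99.4% accuracy for this device's AF detection, so the device may well detect AF by its own algorithm. What remains is a conflict of tachycardia definitions and an unstated AF criterion.

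On size, section 16.22 describes the 1% and 10% as rates of detecting a cardiac event. If the 10% is already a detection rate, discounting it again counts the loss twice. Section 16.2 also makes estimation the stated purpose. Both points are fair, and they are why the figures are illustrative. Nor would it be right to judge the loss by, say, two or more events among the 24 enrolled: the protocol sets no such cut-off, and its power statement is for 18.

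None of this removes the pause and bradycardia contradiction, which no other section resolves.

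**Conclusion.** The contradiction is real and bears on the primary endpoint. For pauses and slow rates, section 11.1 counts episodes outside the explicit storage settings of section 4.0. For tachycardia the two definitions disagree. For AF the storage criterion is missing from the text.

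Followed as written, the plan biases the ICM component of the 12-month rate downward relative to section 11.1. The direction follows from the thresholds, but the size cannot be computed from the documents. The illustrative figures rest on three assumptions: a true rate of 10%, 18 evaluable patients, and a chosen share of event patients with only unrecovered gap episodes. Confidence is high for pauses and bradycardia, and lower for tachycardia and AF, where loss of episodes is possible but not shown. The matter should be settled before the first implant, because episodes that were never stored may not be recoverable later.

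**What to change.** Reconcile sections 4.0 and 11.1 before first implant into one ICM event table that both sections cite. It should cover pause, bradycardia, AV block, tachycardia and AF, each with its rate and duration criterion, so that every ICM event the primary endpoint counts is one the device is set to record. The electrophysiology team chooses the thresholds; this review takes no view on which set is right.

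Add a counting rule: adjudicated episodes that meet the table count toward the ICM component, whether they come from automatic storage, scheduled recordings or post-mortem interrogation. Limiting the count to automatically stored episodes would discard qualifying episodes seen on the scheduled recordings.

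The cost depends on the direction taken. Bringing section 11.1 to the storage criteria needs only wording, plus a stated AF criterion, but gives a narrower ICM endpoint. Widening storage means more strips to review, and is possible only within the device's capability. The documents do not show that the device can record fast runs of every length. Because alerts are acted on clinically, the team should also check whether a change in storage settings would change alerts. Neither route needs additional patients or procedures.
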